5 RANDOMISATION AND ENROLMENT PROCEDURE

5.1 RANDOMISATION PRACTICALITIES

Subjects who meet the relevant criteria and provide informed consent will be randomised to either OC459 or placebo in a 1:1 ratio. Randomisation will occur at a baseline visit after the screening visit(s), and will be in blocks of four in order to balance the number of patients allocated to each treatment group. An unblinded randomisation list (taking into account the blocking requirements) will be generated by Sealed Envelope Ltd and entered into the study database. This file will be password protected, with unblinding instructions provided by the database development team to the investigators.

At randomisation, the database will be interrogated and each new subject assigned the next sequential randomisation item on the list. The unblinded randomisation list will also be provided to the manufacturer, Atopix Ltd, in order to label IMP/placebo appropriately prior to dispensing to pharmacy. Thus the investigators, pharmacy and subjects will all be blinded.

5.2 UNBLINDING

Ceasing treatment rather than unblinding will be encouraged as far as possible. However, where knowledge of the treatment will assist in management of acute illness / emergency treatment, unblinding will be supported. The decision to unblind will be made by the Chief Investigator, with the Trial Steering Committee convened *ad hoc* if necessary to support the decision. Study participants will be provided with a Patient Alert Card indicating the study number and a 24 hour emergency contact number.

Unblinding will take place in line with the standard operating procedure used with the database. Specifically, once the decision has been made to unblind a subject, one of the study team will access the database and enter the subject details and study drug code. As soon as this is entered into the system, an email will be sent to the Trial e-mail address, the trial statistician, the Chief Investigator and the database team warning of a potential unblinding. The essential subject information will be checked against the data in the database and queries raised if they do not agree. The unblinding will not be actioned if there is a discrepancy between the data stored and the data entered. Once this information is accurately completed, a second form must be filled in to confirm the unblinding. The unblinded information will then be displayed, and a second email sent to the Trial e-mail address, the trial statistician, the Chief Investigator and the database team confirming the subject has been unblinded. This email will not continue details of the unblinded treatment. If the site unblinding account has been used, the database support team will set a new, pre-expired password and send new unblinding instructions to the study team.

The Chief Investigator will review the cause and results of the unblinding process with the study team, and possibly the Trial statistician, and document/implement any follow-up actions.

6 TREATMENTS

6.1 TREATMENT ARMS

The Investigational Medicinal Product (IMP) used in the study will be OC459 50mg or matched placebo film-coated tablets. The dose of OC459/placebo will be 50mg (one tablet) to be taken orally, once daily, for 5 weeks in total. Both OC459 and placebo will be manufactured and delivered by Atopix Therapeutics Ltd at no cost to the study. These will be supplied to the pharmacy at St Mary's Hospital to be stored securely.

The identity of the study medications will be blinded and packaged according to the randomisation schedule.

7 INVESTIGATIONAL MEDICINAL PRODUCT (IMP)

7.1 IMP DESCRIPTION

OC459 is a once-daily oral, highly potent and selective CRTH2 antagonist which is active on both the recombinant and native human receptor.

The integrated safety database for OC459 includes data for a total of 754 subjects who received OC459 for up to 3 months with more than 500 subjects receiving doses ≥ 100 mg daily. The overall incidence of adverse events was similar for those treated with OC459 (28.2%) compared to placebo (26.7%) and few subjects in either group had serious adverse events (0.1% and 0.5% for OC459 and placebo respectively). The adverse event profile after OC459 administration was generally comparable to that after placebo; the most common adverse event reported was headache (6.6% vs 5.1% for OC459 and placebo, respectively).

OC459 repeat doses of up to 400mg have been studied in patients and no clear dose ordered effects on safety have been observed. Furthermore, no end organ toxicology or significant changes in clinical chemistry (including liver enzymes) have been observed in non-clinical toxicology studies including long term studies conducted at very high doses in the mouse (3 month dosing), rat (six months dosing) and the dog (12 month dosing). The known metabolites of OC459 have been detected in at least one species including the acylglucuronide of OC459 which is the major metabolite in humans.

7.2 STORAGE OF IMP

Clinical trial supplies will be stored below 30°C, protected from moisture and light, in the pharmacy or other secure area within the investigational site. They must not be frozen or refrigerated. They will be stored in such a way that they cannot be mixed up or confused with other medications, be they clinical trial supplies or medicines for routine clinical use. In addition, returned study medication will not be stored with unused study medication.

7.3 DISPENSING AND ACCOUNTABILITY

A record of study drug movements will be kept to maintain accountability. Only authorised personnel (as designated by the study delegation log) will be allowed to distribute the drugs. Any queries regarding supply should be directed to the study coordinator or the lead trial pharmacist (contact details in the Appendices).

7.4 COMPLIANCE WITH TRIAL TREATMENT

Compliance will be self-reported by participants in their diary cards. In addition, we will collect and count returned tablets at the end of the study. Non-compliance will be defined as $>20\%$ missed doses as per diary cards and/or tablet count at the end of the study. Participants who are non-compliant will be excluded from a per protocol analysis.

7.5 POST-TRIAL TREATMENT

The IMP is unlicensed and therefore will not be made available to participants beyond the end of the study.

8 PHARMACOVIGILANCE

8.1 DEFINITIONS

Adverse Event (AE): any untoward medical occurrence in a patient or clinical trial subject administered a medicinal product and which does not necessarily have a causal relationship with this treatment. *An AE can therefore be any unfavourable and unintended sign (including an abnormal laboratory finding), symptom, or disease temporally associated with the use of an investigational medicinal product (IMP), whether or not considered related to the IMP.*

Adverse Reaction (AR): all untoward and unintended responses to an IMP related to any dose administered. *All AEs judged by either the reporting investigator or the sponsor as having reasonable causal relationship to a medicinal product qualify as adverse reactions. The expression reasonable causal relationship means to convey in general that there is evidence or argument to suggest a causal relationship.*

Unexpected Adverse Reaction: an AR, the nature or severity of which is not consistent with the applicable product information (eg investigator's brochure for an unapproved investigational product or summary of product characteristics (SmPC) for an authorised product). *When the outcome of the adverse reaction is not consistent with the applicable product information this adverse reaction should be considered as unexpected. Side effects documented in the SmPC which occur in a more severe form than anticipated are also considered to be unexpected.*

Serious Adverse Event (SAE) or Serious Adverse Reaction: any untoward medical occurrence or effect that at any dose:

- **Results in death.**
- **Is life-threatening** – *refers to an event in which the subject was at risk of death at the time of the event; it does not refer to an event which hypothetically might have caused death if it were more severe.*
- **Requires hospitalisation, or prolongation of existing inpatients' hospitalisation.**
- **Results in persistent or significant disability or incapacity.**
- **Is a congenital anomaly or birth defect.**

Medical judgement should be exercised in deciding whether an AE/AR is serious in other situations. Important AE/ARs that are not immediately life-threatening or do not result in death or hospitalisation but may jeopardise the subject or may require intervention to prevent one of the other outcomes listed in the definition above, should also be considered serious.

Suspected Unexpected Serious Adverse Reaction (SUSAR): any suspected adverse reaction related to an IMP that is both unexpected and serious.

8.2 CAUSALITY

Most adverse events and adverse drug reactions that occur in this study, whether they are serious or not, will be expected treatment-related toxicities due to the drugs used in this study. The assignment of the causality should be made by the investigator responsible for the care of the participant using the definitions in the table below.

If any doubt about the causality exists the local investigator should inform the study coordination centre who will notify the Chief Investigators. The pharmaceutical companies and/or other clinicians may be asked to advise in some cases.

In the case of discrepant views on causality between the investigator and others, all parties will discuss the case. In the event that no agreement is made, the MHRA will be informed of both points of view.

Relationship	Description
Unrelated	There is no evidence of any causal relationship
Unlikely	There is little evidence to suggest there is a causal relationship (e.g. the event did not occur within a reasonable time after administration of the trial medication). There is another reasonable explanation for the event (e.g. the participant's clinical condition, other concomitant treatment).
Possible	There is some evidence to suggest a causal relationship (e.g. because the event occurs within a reasonable time after administration of the trial medication). However, the influence of other factors may have contributed to the event (e.g. the participant's clinical condition, other concomitant treatments).
Probable	There is evidence to suggest a causal relationship and the influence of other factors is unlikely.
Definitely	There is clear evidence to suggest a causal relationship and other possible contributing factors can be ruled out.
Not assessable	There is insufficient or incomplete evidence to make a clinical judgement of the causal relationship.

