9.14 BRONCHOSCOPY

Bronchoscopies will be performed on study visits as per Table 1 in the endoscopy suite at St Mary's Hospital, in accordance with British Thoracic Society (BTS) guidelines [26]:

- Subjects will sign a consent form on entering the study and will sign a separate consent form for each bronchoscopy. The procedure will be explained during the assessment stage and subjects will be given written information specifically regarding bronchoscopies in addition to the Participant Information Sheet.
- Subjects will fast for six hours prior to the procedure.
- Resuscitation equipment (for intubation, ECG monitoring and defibrillation) and necessary drugs (salbutamol, theophylline, adrenaline, hydrocortisone) will be available in the bronchoscopy room.
- Premedication will be given including:
 - Nebulised salbutamol 2.5mg prior to bronchoscopy
 - Sedation with midazolam (2-10mg) and/or fentanyl (25-200mcg) as necessary
 - Lignocaine spray (10%) and solutions (1%) for topical anaesthesia. The total dose will not exceed 7mg/kg or 400mg in total.
- Supplemental oxygen at a rate of 2Lmin⁻¹ is given via a nasal cannula and oxygen saturations and heart rate are monitored with a pulse oximeter continuously. Intravenous access will be mandatory in all cases.
- The subject will be monitored during the bronchoscopy by a separate nurse and a second suitably qualified physician will be present to act as an advocate.
- The following samples will be collected in this order:
 1. Bronchosorption using Synthetic Absorptive Matrix (SAM)
 2. Bronchial brushings
 3. Bronchoalveolar lavage (BAL)
 4. Bronchial biopsy

At the second bronchoscopy, sampling should be performed on the contralateral side to the analogous procedures done at the first bronchoscopy.

- All adverse events (pain, bleeding, hypoxia etc) will be recorded.
- Subjects will be observed for 1-2 hours, nil by mouth, after the procedure.
- Transportation will be arranged as subjects should not drive on the day of the procedure.
- All subjects will have a contact telephone number on discharge.

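### Protocol 8.2 predicts that most adverse events will be expected and drug-related; this contradicts the safety data in 7.1 and risks biased causality and expectedness judgements

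*Protocol*

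**What the plan says.** Protocol 8.2 (Causality) begins: "Most adverse events and adverse drug reactions that occur in this study, whether they are serious or not, will be expected treatment-related toxicities". It gives the drugs used in the study as the reason. It then asks the responsible investigator to assign causality from a table running from Unrelated to Definitely, with a Not assessable category. Doubtful cases go to the coordination centre, and views that stay discrepant go to the MHRA.

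Protocol 7.1 (IMP Description) summarises a database of "a total of 754 subjects who received OC459 for up to 3 months". It concludes: "The adverse event profile after OC459 administration was generally comparable to that after placebo".

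Protocol 8.1 (Definitions) judges whether a reaction is unexpected by its consistency with the product information, for example the investigator's brochure. It defines a SUSAR as "any suspected adverse reaction related to an IMP that is both unexpected and serious". Protocol 8.3.2 requires a form within 24 hours for every SAE, whatever its cause.

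Protocol 9.14 (Bronchoscopy) foresees harms from the procedure: "All adverse events (pain, bleeding, hypoxia etc) will be recorded".

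SAP Tables 3.25 and 3.29 tabulate events by relationship to study treatment only. SAP 6.3.3 says adverse events are recorded as uncoded free text.

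**The concern.** The sentence stands directly above the causality instructions and tells the assessor what to expect on two separate questions: whether the drug caused the event, and whether the event was foreseen. It includes serious events. For OC459, 7.1 gives no support to either expectation.

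Subjects who complete the schedule also have a live virus challenge and two bronchoscopies while on study medication, so causes other than the drug are built into the design. The causality table offers clinical condition and concomitant treatment as examples of other explanations, but names neither the inoculation nor bronchoscopy. If assessors lean towards drug-related and expected, the relatedness tables lose meaning and the expectedness judgement, on which SUSAR classification depends, may be coloured. Safety is a stated secondary objective in a trial of 44 subjects, so the few events that occur should be attributed as cleanly as possible.

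**Working it through.** **Inputs (Protocol 7.1, OC459 vs placebo).** Any adverse event 28.2% vs 26.7%; SAEs 0.1% vs 0.5%; headache, the most common event, 6.6% vs 5.1%; 754 subjects on OC459. The placebo denominator is not given. Allocation is 1:1 (5.1) with 22 per arm (10.1).

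**The plan's own figures.** Without event counts or a placebo denominator the rates cannot be rebuilt. The OC459 percentages are possible counts: 213/754 = 28.2%, 50/754 = 6.6%, 1/754 = 0.1%.

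**Share of affected subjects in excess of placebo.** With p1 the OC459 rate and p0 the placebo rate, taken as background:

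- OC459 arm, (p1 − p0)/p1: (28.2 − 26.7)/28.2 = 1.5/28.2 = 5.3%.
- Two equal arms together, (p1 − p0)/(p1 + p0): 1.5/54.9 = 2.7%.
- Headache: (6.6 − 5.1)/6.6 = 1.5/6.6 = 23%.
- SAEs: 0.1 − 0.5 = −0.4 points, so no excess.

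At 22 per arm these rates give 22 × 0.282 = 6.2 and 22 × 0.267 = 5.9 affected subjects, an excess of about 0.3 subject.

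**What 'most' would need.** For more than half of affected OC459 subjects to be in excess of placebo, p1 must exceed 2 × 26.7 = 53.4%. For more than half across both arms, p1 must exceed 3 × 26.7 = 80.1%. The stated rate is 28.2%.

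**Sampling error.** I assume a placebo denominator between 187 and 754. The upper 95% limit of the difference is 1.5 + 1.96 × SE points, with SE = √[p1(1 − p1)/754 + p0(1 − p0)/n0]. This gives 8.6 points at n0 = 187 and 6.0 points at n0 = 754, which is 31% and 21% of affected OC459 subjects. Both are below half.

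**Can causes be separated afterwards?**

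- *Timing.* Dosing is daily from day −21 to day 14. The bronchoscopies fall on days −8 and 5 and the inoculation on day 0, so all three lie inside the dosing period. Plausible timing relative to medication, the example given under Possible, therefore does not distinguish the drug from the challenge or the procedure.
- *Phase tables.* I assume weeks are counted from randomisation on day −21. Week 1 of SAP Table 3.23, labelled as before treatment, is then days −21 to −15, already on drug. The assessment phase, weeks 3 to 4, is days −7 to 6, and mixes the last week before inoculation with the first week after it. Follow-up, from week 5, starts on day 7, while dosing continues.
- *Expectedness.* The SAE form contents listed in 8.3.2 do not mention it, although SAP Table 3.26 has a column for it. The protocol names no role to make the judgement.

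**The case against.** The strongest answer is that the sentence forecasts and does not instruct. The next sentence supplies the rule, and the table behind it includes Unrelated and Unlikely, the latter covering another reasonable explanation. Section 8.1 fixes expectedness by the product information, and the sponsor as well as the investigator may judge an event to be a reaction. Every SAE reaches the coordination centre within 24 hours. All of this stands.

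It also rules out a stronger reading that a reader might infer: that serious virus or bronchoscopy events would be misattributed and unexpected drug reactions would escape SUSAR reporting. Nothing tells anyone to assume that an event is expected. The two supposed harms also pull in opposite directions: a procedure-related SAE wrongly called drug-related, and absent from the product information, becomes a SUSAR, which is over-reporting.

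A claim that a true drug signal would be diluted also goes too far. The safety outcome in Protocol 3.1 is the difference in number of adverse events, and SAP Tables 3.23, 3.24, 3.27 and 3.28 compare arms without using relatedness. Assessors are blinded, so over-attribution should affect both arms similarly.

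Nor do the documents show that the virus and bronchoscopy will be the main sources of events: Protocol 1.2 reports no adverse events in the site's earlier challenge studies, and 9.16 no serious ones with this inoculum. The reference to drugs used in the study might include sedation or local anaesthetic, although 8.1 defines reactions by the IMP.

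What remains is the contradiction between 7.1 and 8.2, and attribution records that cannot systematically separate the three sources.

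**Conclusion.** The contradiction is real. On the protocol's own figures about 5% of OC459 subjects with an adverse event are in excess of placebo, and SAEs show no excess. The 5% is a point estimate and counts subjects, not events; it is not a ceiling. Under the assumed placebo denominators the upper limit is 21% to 31%, still short of most. The 7.1 subjects are not described as having had a virus challenge or bronchoscopy, so the figures speak to OC459's contribution and do not predict event rates in this trial.

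The consequence is a risk of biased causality and expectedness judgements and of relatedness tables that say little. The main comparison of event numbers between arms does not depend on the sentence. This is a cheap improvement, not a demonstrated failure of safety reporting.

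**What to change.** Reconcile Protocol 7.1 and 8.2:

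1. Remove or rewrite the opening sentence of 8.2 so that it prejudges neither causality nor expectedness, and refer there to the product-information standard already in 8.1.
2. On the adverse event and SAE forms, record relationship separately to the IMP, to RV-16 inoculation, and to bronchoscopy or another study procedure.
3. Show the three attributions by arm in SAP Tables 3.25 and 3.29.

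The cost is a wording change, two extra form fields per event and extra columns in two tables. The only downside is slightly more form-filling.

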8.3 REPORTING PROCEDURES

All adverse events should be reported. Depending on the nature of the event the reporting procedures below should be followed. Any questions concerning adverse event reporting should be directed to the study coordination centre in the first instance. A flowchart is given below to aid in the reporting procedures.

8.3.1 Non serious AR/AEs

All such toxicities, whether expected or not, should be recorded in the toxicity section of the relevant case report form and sent to the study coordination centre within one month of the form being due.

8.3.2 Serious AR/AEs

Fatal or life threatening SAEs and SUSARs should be reported on the day that the local site is aware of the event. The SAE form asks for nature of event, date of onset, severity, corrective therapies given, outcome and causality (i.e. unrelated, unlikely, possible, probably, definitely). The responsible investigator should sign the causality of the event. Additional information should be sent within 5 days if the reaction has not resolved at the time of reporting.

SAEs

An SAE form should be completed and faxed to the study coordination centre for all SAEs within 24 hours.

SUSARs

In the case of suspected unexpected serious adverse reactions, the staff at the site should:

Complete the SAE case report form & send it immediately (within 24 hours, preferably by fax), signed and dated to the study coordination centre together with relevant treatment forms and anonymised copies of all relevant investigations.

[figure not shown]
Or

Contact the study coordination centre by phone and then send the completed SAE form to the study coordination centre within the following 24 hours as above.

The study coordination centre will notify the MHRA, REC and the Sponsor of all SUSARs occurring during the study according to the following timelines; fatal and life-threatening within 7 days of notification and non-life threatening within 15 days. All investigators will be informed of all SUSARs occurring throughout the study.

Local investigators should report any SUSARs and /or SAEs as required by their Local Research Ethics Committee and/or Research & Development Office.

Safety Reporting Overview

Contact details for reporting SAEs and SUSARs

[contact], attention [name]

Email: [contact]

[contact] (Mon to Fri 09.00 – 17.00)

9 ASSESSMENT AND FOLLOW-UP

9.1 SUMMARY OF STUDY ASSESSMENTS AND PROCEDURES

After screening and providing informed consent, eligible participants will undergo baseline investigations and randomisation, followed by a 21 day run-in period on placebo or OC459. Towards the end of this period they will have a baseline bronchoscopy and other investigations. At the end of the run-in period, subjects will have a further set of investigations prior to rhinovirus inoculation the same day. Regular sampling and assessments will take place as indicated whilst treatment administration continues uninterrupted for a further 14 days, for a total of 5 consecutive treatment weeks. Trial medications are then stopped (day 14). Subjects will attend for a final follow-up visit 4 weeks later with convalescence investigations (day 42). Table 1 summarises subject visits and procedures during the study. Details of the individual study procedures are listed below.

Study participants will be seen frequently during the study period, daily if they wish. They have details to contact the Clinical Research Fellow and Clinical Research Nurse, and will be offered daily telephone contact. In this way participants will be assessed regularly by the investigating team and any adverse events detected rapidly. When the study is completed, subjects will return to the care of their GP (they will not be routinely followed-up by the study group).

	Screening visit 1	Screening visit 2	Visit 1 (baseline)	Visit 2	Visit 3	Visit 4	Visit 5	Visit 6	Visit 7	Visit 8	Visit 9	Visit 10	Visit 11
Study day			-21	-9	-8	0	2	3	4	5	7	10	42
Ideal weekday			F	W	T	F	Su	M	T	W	F	M	F
Visit length	30 min	60 min	60 min	45 min	3 hr	60 min	45 min	45 min	45 min	3 hr	60 min	45 min	30 min
Skin prick test	X												
Viral serology	X												X
Asthma Control Questionnaire (ACQ)	X		X	X		X						X	X
Spirometry (in clinic)	X		X	X		X	X	X	X	X	X	X	X
Histamine challenge (PC ₂₀)		X	X	X							X		
Exhaled nitric oxide (FeNO)		X	X	X		X		X		X	X	X	X
Blood tests		X	X		X			X		X		X	X
ECG		X											
Urine pregnancy test		X											
Chest radiograph		X											
IMP or placebo administration			Daily from day -21 → day 14 (then stop)										
Nasosorption			X			X	X	X	X	X	X	X	
Nasal lavage			X			X	X	X	X	X	X	X	
Nasal scrape			X		X			X		X			
Bronchoscopy (bronchosorption, BAL, brushings, biopsies)					X					X			
Sputum induction			X	X					X		X		
Virus inoculation						X							
Symptom diaries including spirometry and medication			Daily at home during study period →										
Spirometry (portable, at home)			Daily at home during study period →										

Table 1: Summary of study visits and key procedures

